5.12.13.2 Study Endpoints

Primary efficacy parameters:

- Change of body weight (kg) between day 1 and day 7
- Change of IGF-1 plasma levels between day 1 (prior to dose) and day 7
- Change of quality of life score (Anderson Symptom Assessment Scale, FACIT-F) between day 1 and day 7

Secondary efficacy parameters:

- Food intake as measured by a food diary to be recorded for 3 days before days 1 and 7 and by a test meal administered at screening and on day 7.
- Change of appetite measured by a validated visual analogue scale between day 1 and day 7.
- Body composition as measured by bio-impedance on days 1 and 7.
- Muscle strength as measured by handgrip strength and stair climbing power.
- Energy expenditure as measured by indirect calorimetry.

- Change in GH, IGFBP-3, CRP, IL-6 and TNF- α and glucose between day 1 and day 7.
- Changes in reward from food as measured by brain functional Magnetic Resonance Imaging (fMRI).
- Changes in functional brain connectivity as assessed by Resting State Functional Connectivity (RSFC) imaging and Diffusion Tensor Imaging (DTI).

Safety parameters:

- Clinical laboratory parameters: complete blood count (CBC), comprehensive metabolic panel (CMP), urinalysis (UA)
- Vital signs,
- Electrocardiogram (ECG) changes pre and post-dosing at day 1 and day 7 and on the post-study visit.
- Recording of adverse events from day 1 to day 7

5.12.13.3 Statistical Analyses

Safety, including adverse events, ECGs, vital signs, and laboratory assessments will be summarized by treatment group. All safety analyses will be performed on the ITT population. For continuous variables, descriptive statistics including the number of observations (N), mean, standard deviation, minimum, and the maximum will be presented for the values as well as for the change from baseline by treatment group at each time point. Treatment-emergent adverse events (TEAEs) are defined as those adverse events that start on or after the first dose of randomized study drug. The number and percent of patients reporting TEAEs, grouped by MedDRA system organ class and preferred term, will be tabulated by treatment group. Summaries will also be provided by maximum severity for the number and percentage of patients with TEAEs and for patients with drug-related TEAEs by system organ class, preferred term, and treatment group. Serious adverse events and adverse events leading to discontinuation will be summarized in a similar fashion. Vital signs at each time point and changes from baseline will be summarized by treatment group. Laboratory results of interest will be summarized by treatment group using frequencies and percentages. MRI has been repeatedly shown to be extremely safe. In fact, there is no reason to believe that the scanners can cause any undesirable effect. Safety precautions, however, are very important. The scanners are very strong electromagnets and any piece of metal inside the scanner room could potentially be a hazard. We are equipped with metal detectors (both in the room's door and wand style) and extensively query patients about the possibility of metals inside their bodies (pins, staples, etc).

5.12.14 Withdrawal of Participants

It is unlikely that participants will be withdrawn without their consent. This may happen if the sponsor or regulatory authorities (VA) decide to terminate the study. Participation is completely voluntary and patients may withdraw from this study at any time without any negative consequences or penalty for study withdrawal. To withdraw, patients will be instructed to advise study staff directly by calling the number in the consent form. The participant will not have the option to get the remaining portion of their sample back. Samples will not be destroyed but the sample will be kept anonymously and used for analysis. Patients may withdraw their consent and discontinue at any time with verbal or written notification to the investigators. Patients will be encouraged to complete the final endpoint and post-study visit procedures if possible.

6.0 Reporting

The Investigator is responsible for monitoring the safety of patients who have enrolled in the study. The investigator will grade adverse events using the NCI-CTCAE, Version 4 (Appendix I). All adverse events occurring after any administration of the study drug through the 16 day post-treatment follow-up visit will be followed until the event resolves, until the patient begins alternative. However, certain adverse events (e.g., a cerebrovascular accident, worsening hypertension) will not be expected to resolve completely; in these cases, the date and time should be recorded when the event reaches its new, stable equilibrium and any remaining residua of the event should be documented.

The investigator is required to document all adverse events occurring during the clinical trial, commencing with the first dose of study drug through the 16 day post-treatment follow-up visit. Adverse events occurring following the signature of the informed consent, but prior to the first dose of study drug will not be reported as adverse events, but will be captured as medical history. The adverse event reporting period also ends if the patient begins an alternative therapy within 16 days of the last administration of study drug. It is also important to record all adverse events that result in permanent discontinuation of Macimorelin, whether serious or non-serious. All serious adverse events will be reported within 24 hours of study staff being made aware of the event, to AEZS. All serious adverse events will be reported within 7 calendar days of study staff being made aware of the event to FDA for fatal or life-threatening events and within 15 calendar days of study staff being make aware of the event to FDA for all other serious adverse events. Serious adverse events will also be reported within 5 business days of study staff being made aware of the event to IRB per posted guidelines (immediate oral notification will be made to IRB in the case of local death). The DMC will be notified via secured email according to the same regulations as reporting to IRB.

Any untoward or unfavorable event occurring following administration of study drug, whether or not it is considered to be related to the study drug will be considered an adverse event (AE). An AE can therefore be any unfavorable and unintended sign, symptom, or disease temporally associated with the use of a medicinal (investigational) product, whether or not considered related to the medicinal (investigational) product. All AEs, including observed or volunteered

problems, complaints, or symptoms, are to be entered into the paper CRFs. Each AE is to be evaluated for duration, intensity, and causal relationship with the study medication or other factors. A non-serious AE is any untoward medical occurrence that does not meet any of the criteria for serious AEs. A worsening of a pre-existing condition will be considered an AE as well. A pre-existing condition which occurs with a known temporal frequency and severity (e.g., dysmenorrhea) following drug exposure will not be considered an adverse event unless the pattern or severity has changed.

Patients should be instructed to report any AE that they experience to the Investigator. The investigator should assess for AE at each visit. AEs occurring during the clinical trial and the follow-up period should be recorded. To capture the most potentially relevant safety information during a clinical trial, it is important that the investigator record accurate AE terms on the paper CRFs.

Whenever possible, a specific disease or syndrome rather than individual associated signs and symptoms should be identified by the Investigator and recorded. However, if an observed or reported sign or symptom is not considered a component of a specific disease or syndrome by the Investigator, it should be recorded as a separate adverse event.

- **Seriousness:** A serious adverse event (SAE) is any AE that: results in death, permanent or significant disability, hospitalization or a prolongation of an existing hospitalization; is a congenital anomaly/birth defect; or is otherwise medically alarming.
- **Severity:** All adverse events will be rated according to the National Cancer Institute (NCI) Common Toxicity Criteria (CTCAE v4.0, Appendix I).
- **Relationship to Study Drug:** All adverse events will be assessed by the Investigator to establish the presumed causal relationship with the study drug considering: a) Temporal relationship, b) Pattern consistent with known drug effect and c) Presence of other potential etiologies. Adverse events will be assigned one of the following causal relationships:
 - **Unrelated:** The study drug almost certainly (or certainly) did not cause the event. Guidelines: There is no reasonable temporal relationship of the event to the administration of drug; the pattern is inconsistent with that known for the drug; and/or there is another obvious etiology.
 - **Probably not related:** It is more likely that the event is due to another etiology than due to the study drug. Guidelines: There is no reasonable temporal relationship of the event to the administration of drug; the pattern is inconsistent with that known for the drug; and/or there is another more likely etiology.
 - **Possibly Related:** It is equally likely that the event is due to the study drug as it is due to another etiology. Guidelines: There is a reasonable temporal relationship of the event to the study drug; the drug seems as likely as other etiologies to have caused the effect.

- **Probably Related**: It is more likely that the event is due to the study drug than due to another etiology. Guidelines: There is a reasonable temporal relationship of the event to the study drug; the event may be consistent with a known pattern of drug (or drug class) effects; the drug seems more likely than other etiologies to cause the effect; the adverse event diminished upon cessation of study drug exposure or reduction in dose; and/or the adverse event worsened or recurred upon unintentional re-exposure to the study drug (Intentional rechallenge for the purpose of assigning causality should not be performed).
- **Definitely Related**: The evidence is compelling that the study drug caused the adverse event. Guidelines: there is a reasonable temporal relationship of the event to the study drug; the event is consistent with a known pattern of drug (or drug class) effects; the drug is far more likely than other etiologies to have caused the effect; the adverse event diminished upon cessation of study drug exposure or reduction in dose; the adverse event worsened or recurred upon unintentional re-exposure to the study drug (Intentional rechallenge for the purpose of assigning causality should not be performed).
- **Unknown**: The data are inadequate to assign any of the above causal relationship categories to the study drug.
- **Monitoring Adverse Events**: Patients will be monitored for the onset of AEs throughout the course of the study from the time of first exposure to the study drug until the post-study visit. Any ongoing AE will be assessed at appropriate frequency to document the date and time of resolution of the event. All events will be followed to resolution even if ongoing at the post-study visit. Certain AEs (e.g., a cerebrovascular accident) will not be expected to resolve completely; in these cases, the date and time will be recorded when the event reaches its new, stable equilibrium and any remaining residua of the event will be documented. All AEs will be followed until resolution or until stable in cases where permanent sequelae are expected.
- **Serious Adverse Event Reporting**: A SAE (per 21 CFR §312.32) is any adverse experience occurring at any dose that results in any of the following outcomes:
 - Death
 - A life-threatening adverse drug experience
 - Inpatient hospitalization or prolongation of existing hospitalization
 - A persistent or significant disability/incapacity
 - A congenital anomaly/birth defect

All serious adverse events will be reported within 24 hours of study staff being made aware of the event, to AEZS. All serious adverse events will be reported within 7 calendar days of study staff being made aware of the event to FDA for fatal or life-threatening events and within 15 calendar days of study staff being make aware of the event to FDA for all other serious adverse events. Serious adverse events will also be reported within 5 business days of study staff being made aware of the event to IRB per posted guidelines

(immediate oral notification will be made to IRB in the case of local death). The DMC will be notified via secured email according to the same regulations as reporting to IRB. This reporting requirement is mandatory regardless of whether the event is considered to be drug related or not.

Important medical events may be considered an SAE based upon appropriate medical judgment. They may jeopardize the patient(s) and may require medical or surgical intervention to prevent one of the outcomes listed above. For all SAEs occurring during the study or within 16 days of the last administration of study drug, the Investigator must submit follow-up reports to AEZS or its representative regarding the status of the SAE and the patient's subsequent course until the SAE has subsided, or until the condition stabilizes (in the case of persistent impairment), the patient receives alternative therapy, or the patient dies. Follow-up reporting is done by faxing in SAE follow up reports.

AEZS must also be notified of any patient who becomes pregnant or their partner who becomes pregnant, while participating in a clinical trial. The Investigator must immediately notify the IRB and AEZS of any pregnancy associated with study medication exposure (at least 6 half-lives after drug administration) and record the event. Protocol-required procedures for study discontinuation must be performed on the patient unless contraindicated by pregnancy. All pregnancies must be followed to conclusion to determine their outcome. Infants should be followed for a minimum of 8 weeks.

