5.0 Study Procedures

5.1 Study Design

This is a double-blind, randomized, placebo-controlled trial to test the effects of the ghrelin mimetic macimorelin in cancer-cachexia patients after one week of administration. Adequate efficacy will be defined as a ≥ 0.8 kg of body weight gain or a ≥ 50 ng/mL increase in plasma IGF-1 levels or an improvement in quality of life questionnaires of at least 15% compared to placebo. The timeline of the study procedures are as follows:

	Screening: Day -24 to Day -1	Baseline: Day 1	Day 7: assessment/end of treatment	Post-study visit: 14 +/- 3 days after end-of-treatment
Informed Consent	X			
History and exam¹	X	X	X	X
AEZS-130 administration		X	X	
PD²		X	X	
ECG and Safety Labs³	X	X	X	X
Body Composition Analyses⁴		X	X	

Functional performance assessment⁵		X	X	
Resting energy expenditure⁶		X	X	
Questionnaires⁷		X	X	
Laboratory assays⁸		X	X	
Appetite and food intake assessment⁹	X		X	
MRI	X		X ¹⁰	
Adverse Events		X ¹⁰	X	X

Footnotes: Patients will receive treatment daily between days 1 and 7. Dosing on days 1 and 7 will take place in the clinic. Patients will take the drug at home on days 2-6. All tests will be done before dosing unless otherwise noted.

¹ Exam will include body weight measurement and a complete physical exam.

² Pharmacodynamics (PD) will be assessed before and 1 hour after dosing with measurements of GH.

³ Safety labs will include: CBC with Diff, comprehensive metabolic panel, and UA (including hCG for females). On days 1 and 7 ECG will be performed before and 1h after dosing.

⁴ Tests include bioimpedance analysis and dual energy x-ray absorptiometry.

⁵ Functional performance will be assessed by: a) handgrip strength, b) stair climbing power, c) activity level

⁶ Resting energy expenditure will be assessed by indirect calorimetry.

⁷ Questionnaires will include: The Eastern Cooperative Oncology Group (ECOG), and Karnofsky Scales, Anderson Symptom Assessment Scale (ASAS) and Functional Assessment of Chronic Illness Therapy-Fatigue (FACIT-F).

⁸ This will include measurements of glucose, IGF-1, GH, IGFBP-3, IL-6, CRP, and TNF-alpha.

⁹ Appetite will be assessed by a VAS before and 1h after breakfast; food intake will be assessed by a food diary. A test meal will be given at screening and 1h after dosing on day 7.

¹⁰ After dosing

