- After informed consent but before the test meal is given, patients' brains will be imaged in a Phillips 3T scanner. Before starting the experiment, an investigator or trained technician will give the patient instructions on the safety of the MRI scan. The MRI scanner we will use differs from conventional scanners only in that the magnet strength is 3.0 T, rather than the more typical 1.5 T magnets used in routine clinical scanning. The patient will enter a large room where a powerful magnet is located. Patient will be instructed to remove all jewelry and other metal-containing objects. The patient will then be placed on a narrow table with plastic-encased metal coil close to the head. Next, the patient will be slid into a small tunnel approximately 6 feet long and 25 inches in diameter. The duration of the scan is approximately 30 minutes. A small mirror will be positioned above the patient's head so the other end of the scanner is visible. After the patient is positioned, the table will move the patient into the scanner itself. The patient will be in voice-communication with a technician or investigator via an intercom, and will have access to a squeeze bulb that generates a loud noise just in case the patient would like to be withdrawn at any point. Each patient will undergo two scanning sessions (pre and Day7 macimorelin or placebo). A computer display will be positioned at one end of the scanner and can be seen through the mirror above the patient's head. Patients will be asked to allow us to put one or two small, soft, rubber tubes, similar to straws, into his/her mouth. The tubes will be used to give patient small squirts of a flavored beverage while in the scanner. Patients will simply swallow, while keeping his or her head still. Patients will be given a CD with .gif images of their brain taken during the structural scan if it is their first time being scanned.

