- Body composition will be measured by BIA and DXA before dosing. BIA is a noninvasive method of estimating body composition based on the ability of tissues to conduct an electrical current. Based on this principle, lean tissue conducts electricity better than fat; therefore, the body composition analyzer/scale is able to calculate total body water, total body fat and total body lean mass. DXA scan uses a low amount of radiation to determine fat mass and bone mass and calculates fat-free mass (whole body and segmental).
- Functional performance will be assessed before dosing by: a) HGS and b) SCP. These tests have been shown to correlate with VO_2 max and are good tests of aerobic and functional capacity in cachectic states (41, 42). Briefly, HGS will be measured by a handheld dynamometer (Jamar Hydraulic Dynamometer, J.A. Preston Corp., Clifton, NJ) as described elsewhere (43). SCP, which allows measuring the

maximal anaerobic power of the involved muscles, will be performed as follows. At the moment of the first execution, 2–3 practice trials will be allowed so that the patients gained a good control of the performing technique. SCP consists in a modification of the test proposed by Margaria et al, (44), recently applied in elderly patients (45). In brief, patients will be invited to climb up ordinary stairs at the highest possible speed, according to their capabilities. The stairs will consist of 13 steps of 15.3 cm each, thus covering a total vertical distance of 1.99 m. An experimenter will measure the time employed to cover the test with a digital stopwatch. In line with Margaria et al. (44), assumptions, anaerobic power (in W) will be calculated by using the following formula: "body mass x 9.81 x vertical distance/time where body mass, vertical distance (i.e., 1.99 m) and time are expressed in kg, m and s, respectively, and 9.81 m/s² represents the acceleration of gravity. Physical activity will be monitored from Day 1 to Day 7 with the Actical Version 3.0 activity monitor (Respironics Inc., Murrysville, PA). The wrist-worn monitor will be provided on Day 1, along with verbal instructions for proper use, and worn for the entire 7-day study period until it is returned to study staff on the Day 7 visit.

- Previously validated questionnaires including the ECOG and Karnofsky scales will be administered. Patients will also complete the ASAS and FACIT-F questionnaires to assess changes in symptoms that play a role in performance such as fatigue.

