5.11.2 Exclusion Criteria

1. Obesity (body weight >140 Kg);
2. Recent active excessive alcohol or illicit drug use;
3. Severe depression as determined by the investigator;
4. Other causes of cachexia such as: Liver disease (AST or ALT > 3x normal levels); renal failure (creatinine > 1.5 mg/dL), untreated thyroid disease, class III-IV CHF, AIDS, severe COPD requiring use of home O₂;
5. Inability to increase food intake (e.g., esophageal obstruction, intractable nausea and vomiting);
6. Any condition that would prevent the patient from performing the research procedures (e.g., unstable coronary artery disease);
7. Use of growth hormone, megestrol, Marinol, or any other anabolic agents, appetite stimulants, tube feeding, or parenteral nutrition during the 1 month prior to entering the study;
8. Systemic corticosteroids administration for > 6 days a month (i.e.daily continuous schedule).
9. Recent administration (less than 1 week) of highly emetogenic chemotherapy (Hesketh scale class 4-5); patients may otherwise be undergoing chemotherapy.
10. Being female and pregnant, breast-feeding or of childbearing potential. (Note: Lack of childbearing potential for female patients is satisfied by: a) being post-menopausal; b) being surgically sterile; c) practicing contraception with an oral contraceptive, intra-uterine device, diaphragm, or condom with spermicide for the duration of the study; or d) being sexually inactive. Confirmation that the patient is not pregnant will be established by a negative urine hCG pregnancy test at the time of enrollment.
11. Co-administration of drugs that prolong QT interval (Appendix II), CYP3A4 inducers (Appendix III), QTc equal to greater than 450ms at screening or other investigational agents (a wash-out period of five times the half-life of drugs that prolong QT will be allowed with approval of prescriber).
12. Conditions that would preclude from successfully scanning patients in MRI: a. Claustrophobia (this would make lying in the scanner very uncomfortable); b. having a pacemaker, aneurysm clips, neurostimulators, cochlear implants, metal in eyes, steel worker, or other implants; c. History of Seizures; d. History of head injuries resulting in loss of consciousness > 10 minutes.

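### Serious or procedure-caused events between consent and first dose are classed as medical history, with no stated grading, causality assessment or route to the IRB or DMC

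*Combined protocol and SAP*

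**What the plan says.** Section 6.0 has AE documentation begin with the first dose. Events after consent but "prior to the first dose of study drug will not be reported as adverse events, but will be captured as medical history". Its definitions follow the same line. An AE is "Any untoward or unfavorable event occurring following administration of study drug", whether or not related to the drug, and "A serious adverse event (SAE) is any AE that" meets a listed seriousness criterion. The item on monitoring starts at first exposure to study drug. The causality categories rate relation to study drug only.

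The schedule in 5.1 agrees: the Adverse Events row has no entry at screening, and the Day 1 entry carries the footnote for after dosing. Section 5.12.13.3 defines treatment-emergent adverse events (TEAEs) from the first dose onward.

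Several trial procedures come earlier than that:

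- **MRI.** Section 5.5 places the first of two sessions at screening, after consent. Section 5.12.13.3 regards MRI as very safe but notes that "any piece of metal inside the scanner room could potentially be a hazard".
- **Stair climb.** In 5.6, "patients will be invited to climb up ordinary stairs at the highest possible speed", as far as they are able, before dosing on Day 1, with two or three practice trials permitted. The general footnote in 5.1 is "All tests will be done before dosing unless otherwise noted".
- **Wash-out.** Exclusion 11 in 5.11.2 states that "a wash-out period of five times the half-life of drugs that prolong QT will be allowed with approval of prescriber".

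**The concern.** This is a pilot whose stated purpose includes safety, and 2.5 gives safety first place. Yet the same fall on the stairs is an AE on Day 7 and an item of medical history on Day 1. The same holds for an incident in the scanner on Day 7 and at screening.

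The label matters because grading, causality assessment and expedited reporting all attach to the words AE and SAE. A serious event at the screening scan, at the pre-dose stair climb or during a wash-out made to qualify would start none of the reporting clocks in 6.0. The IRB and DMC could learn of it late or not at all, while further patients go through the same step. With about eight patients, one such event would weigh heavily in any judgement of risk and benefit.

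**Working it through.** The plan gives no figure to reproduce on this point. The check is a reading of linked definitions, followed by a count.

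**Step 1: is there another route to reporting?**

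| Place | Text in brief | Reaches a pre-dose event? |
|---|---|---|
| 6.0, reporting period | Starts at first dose; earlier events go to medical history | No |
| 6.0, AE definition | Must follow study drug | No |
| 6.0, Seriousness | An SAE must be an AE | No |
| 6.0, Monitoring Adverse Events | From first exposure | No |
| 6.0, causality scale | Study drug only; no category for procedures | No |
| 5.1 schedule | No AE entry at screening; Day 1 entry after dosing | No |
| 6.0, general AE text and SAE follow-up reports | Looser wording: during the trial or study | Unclear, but depends on the definitions above |

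The reporting clocks are 24 hours to the drug supplier, 7 or 15 calendar days to the FDA, and 5 business days to the IRB, with the DMC notified as for the IRB. All are triggered by an SAE. The immediate oral notice of a local death stands inside the same SAE provision.

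**Step 2: trial procedures in the window, per patient**

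- MRI (5.5, 5.7): 1 before dosing, 1 on Day 7. Share before dosing: 1/2 = 50%. With eight patients each scanned twice, that is 8 of 16 sessions.
- Scored stair climbs (5.6, 5.7): 1 before dosing, 1 on Day 7. Share: 1/2 = 50%.
- All climbs, if the practice trials are used: (2 + 1)/(2 + 1 + 1) = 3/4 = 75% with two, and (3 + 1)/(3 + 1 + 1) = 4/5 = 80% with three. Practice trials are optional and are not described as maximal, so 50% is the figure for maximal effort.

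**Step 3: length of the window**

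- Screening: up to 24 days (5.1) or 3 × 7 = 21 days (5.5). The two do not agree.
- AE period: 7 days of treatment plus 14 ± 3 days (5.1), so 7 + 11 = 18 to 7 + 17 = 24 days.
- Share of the longest time on study outside AE reporting: from 21/(21 + 24) = 47% to 24/(24 + 18) = 57%.

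**Step 4: wash-out**

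Five half-lives fit inside screening only if the half-life is at most 21/5 = 4.2 days or 24/5 = 4.8 days. A longer wash-out would have to start before the screening window. The documents do not say whether wash-out starts before or after consent. If it starts before, the sentence in 6.0 on events after consent does not cover that part, but the AE definition still excludes it.

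**Step 5: effect on the comparison of arms**

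Events before the first dose cannot be caused by study drug, and the TEAE definition leaves them out of both arms alike. The TEAE tables are therefore not biased by this rule.

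**The case against.** The strongest defence is that the safety objective in 3.3 concerns the tolerability of one week of macimorelin, and that a first-dose start is applied consistently in 5.1, 5.12.13.3 and 6.0. That stands for the drug-safety tables, which need no change. It does not answer who is told of a serious event caused by a trial procedure.

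The defence can also point to wording in 6.0 on events during the study, to the IRB's posted guidelines, which are not in the documents, and to the DMC's broad remit in the synopsis. These may help in practice. But the looser wording does not override the definitions, the guidelines are invoked only for SAEs, and the remit is not a reporting route.

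Safeguards exist: metal detection and questioning before MRI (5.12.13.3), permitted use of the handrail (5.12.9), and exclusion of patients whose condition would prevent the procedures (5.11.2). They lower the chance of harm but do not create a reporting path.

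A reader might infer more than the documents support:

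- **That the events go uncollected.** They are captured as medical history, and a full history and examination is repeated on Day 1.
- **That most maximal climbs fall in the window.** Among scored climbs it is half.
- **That every wash-out lies wholly in the window.** Its start relative to consent is not stated.
- **That the SAE wording about any dose sets the limit.** That phrase reads more naturally as dose level. The limit comes from the AE and SAE definitions.
- **That trial-caused harm becomes the baseline.** Section 6.0 counts a pre-existing condition as an AE if it worsens, so this could happen, but it is an inference.

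**Conclusion.** The point holds as a gap in capture and escalation. For up to 21 or 24 days plus the pre-dose part of Day 1, a serious or procedure-caused event has no stated grading, causality assessment or path to the IRB or DMC. That window holds half of the MRI sessions, half of the scored maximal-speed climbs, any practice climbs, and any wash-out to the extent that it follows consent.

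This rests on reading the AE and SAE definitions in 6.0 as governing the looser phrases elsewhere in that section, and on no unseen local rule filling the gap. The documents show no actual harm, and a claim that the comparison between arms is distorted would be wrong. The change is worth making because it serves patient safety at low cost.

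**What to change.** In 6.0, replace the sentence on events before the first dose. From consent to first dose, record as pre-treatment adverse events (a) all serious events and (b) any event attributable to a study procedure or to a wash-out made for the study. Report the serious ones to the IRB and DMC on the timelines already stated. Other intercurrent events may remain medical history. List the pre-treatment events separately, so that the TEAE definition in 5.12.13.3 stays as it is.

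Changing that sentence alone would leave the protocol in conflict with itself. Matching edits are needed to:

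- the AE and SAE definitions in 6.0;
- the causality categories in 6.0, adding relation to a study procedure;
- the monitoring start in 6.0;
- the schedule in 5.1, with an AE entry at screening and before dosing on Day 1;
- the paragraph in 6.0 on SAE follow-up reports, so that its reference to the study matches the new start.

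The protocol should also say whether a wash-out may begin before consent, so that (b) can be applied, and should reconcile the screening length in 5.1 with that in 5.5.

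The cost is a handful of linked text edits and a case report form entry, a few extra listings, and some reports of background cancer events unrelated to the trial. No analysis changes.
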